## **7 RISKS AND BENEFITS**

### **7.1 Ethical considerations**

The Chief Investigator will abide by the ethical principles underlying the Declaration of Helsinki (1996) and good clinical practice (GCP) guidelines on the proper conduct of research, and comply with research governance.

Investigators will hold honorary contracts or research passports, will be trained in GCP, Data Protection, GDPR and will hold current DBS checks. The team includes clinically experienced addiction staff who can immediately deal with any issues arising from this study, as well as link with support from the clinical teams managing the clinical care of opiate dependent participants.

All opiate dependent participants will be engaged with a specialist clinical service for their community based detoxification. They will therefore be receiving support and know how to access extra support if required. The risk of relapse to on-top opiate use is a common challenge faced by individuals in this indication. However, significant instability is less likely in those who are on stable doses of methadone, or those who are tapering or preparing to undertake detoxification. Further, if an individual feels they may relapse, additional support is provided and reduction in their methadone is generally suspended. In this case, we would wait until the risk of on-top use was reduced and their stability or gradual reduction in methadone dose was resumed. The clinical team will have the opportunity to raise with the research team if there are concerns about any participants' suitability to take part in the study or change in circumstance post-screening. Further the PI, [name] is a Consultant addiction psychiatrist with over 20yrs experience in this field and the research team also have several years' experience working with this population.

#### **7.1.1 Potential Risks**

No treatment is withheld from participants in this study and testing will be performed at times convenient to all persons.

Some participants may find the long experimental study day tiring. We will endeavour to take all steps to ensure comfort and provide appropriate rest and sustenance during these procedures.

In our previously completed study (Durant et al 2018) a few of our healthy volunteers and abstinent alcohol dependent individuals reported minor side effects to the 60mg dose of baclofen, primarily dizziness and, nausea. These side effects resolved and all participants were fit to be discharged by end of the study day. The 90mg dose resulted in more pronounced sedation in one healthy volunteer with mild effects still felt the following day so we did not proceed with testing any further healthy participants at this dose. No such effects were seen in the alcohol dependent group and no significant

cardiovascular effects (e.g. blood pressure, heart rate) were observed in either group. The model in this proposal will mitigate risks of giving such high doses if sedation is seen at lower baclofen doses.

We are carefully monitoring for any signs of respiratory depression and such information will be utilised in the model to determine the next safe dose combination. We have enhanced assessments of possible respiratory impairment in our screening protocol so that anyone at risk of respiratory depression is excluded.

### ***7.1.2 Potential Benefits***

Research participants will not directly benefit from taking part but the information we get might help improve the treatment of people with opiate dependence in future. Participants will receive feedback if requested about all aspects of the study, but this will not be available until the end of the study as this is a research investigation and the clinical relevance of the measures taken is not proven.

## **8 STATISTICS AND DATA ANALYSIS PLAN**

### **8.1 General statistical principles**

No formal statistical testing will be conducted for this early phase study and no power calculation has been performed; all statistical analyses for primary and secondary outcomes are to be viewed as exploratory.

### **8.2 METHODS OF RANDOMISATION**

The randomisation schedule will be generated by Sealed Envelope, or independent statistician, using a 3:1 ratio (baclofen: placebo). Blocked randomisation will be used to maintain the 3:1 ratio throughout the study.

### **8.2 SAMPLE SIZE**

The sample size in Phase I is not fixed. Up to a total of 64 patients are planned to be enrolled in the study with up to 48 patients on the experimental baclofen doses and 16 on placebo with a 3:1 allocation ratio. The final sample size will depend on the escalation/de-escalation decisions made using the trial and on the recommendation of the model on stopping earlier. The performance of the Bayesian design based on 48 participants was assessed via simulations under several clinically relevant scenarios in terms of accuracy of the number of patients that would receive (i) their individual target dose combination and (ii) a combination that is safe for them in the subsequently planned phase 2 trial.

### **8.3 STATISTICAL ANALYSIS PLAN**

#### **8.3.1 Analysis sets**

##### **8.3.1.1 Full analysis set**

The full analysis set includes all randomised patients. This is equivalent to the ITT (intent-to-treat) population. The Full analysis set will be used to summarise study conduct and patient disposition.

##### **8.3.1.2 Safety set**

The safety analysis set will consist of all subjects who are randomised and received study drug. Subjects in this analysis set will be used for demographic, baseline characteristics, and safety summaries. Patients will be grouped according to actual treatment received.

##### **8.3.1.3 DLT evaluable safety set**

The DLT evaluable safety analysis set will consist of all subjects who are randomised and received study drug and are evaluable for a DLT. Subjects in this analysis set will be used for the primary dose-combination toxicity response analysis (included in the Bayesian analysis model). Patients will be grouped according to actual treatment received.

The analysis set for each secondary outcome will be based on the subset of patients from the safety set for whom at least 1 measurable outcome has been obtained.

### **8.3.2 Primary analysis**

The first phase I cohort (4 patients) will be randomised to 10mg of baclofen or placebo (3:1 allocation ratio) with subsequent planned dose escalation of baclofen up to 90mg. The escalation will occur only in the case of acceptable safety and tolerability at the next lowest dose of baclofen for the prescribed dose of methadone and if no DLTs are observed for the current cohort of patients. Doses of baclofen cannot be skipped. The relationship between the doses of baclofen and methadone and the probability of observing a DLT will be modelled via a 5-parameter Bayesian logistic regression model with an interaction parameter (Neuenschwander B, 2015). The model will be sequentially updated after at most every 3 patients using the DLT/no DLT data from all previous cohorts in the trial before making the recommendation for the next cohort.

Dose escalation will be based on the review of safety data during the experimental visit on the DLT evaluable safety set. For each given patient with a prescribed dose of methadone, the doses of baclofen are deemed to be safe if the risk of dose-limiting toxicity (DLT) being at least 25%, is less than 25%. The recommendation of the model will be to assign patients in the next cohort to their individual safe doses of baclofen that are more likely to have a toxicity risk of between 15% and 25% according to their prescribed dose of methadone (subject to the escalation constraints above). The patients in the next cohort can receive different doses of baclofen depending on their individual doses of methadone and previous data contributing to the model.

The model can recommend stopping the trial earlier with all doses of baclofen found to be safe, if the probability that the risk of toxicity at 90mg baclofen in combination with 120mg methadone is 25% or below, is above 92.5%. The trial can be recommended to be stopped earlier for safety concerns if the probability that the risk of toxicity at 30mg baclofen in combination with 60mg methadone (the lowest clinically viable combination) being above 25%, is 25% or more.

Further details of the specification of the 5-parameter Bayesian logistic regression model are provided in the detailed Statistical Analysis Plan (SAP) that will be agreed by the TSC.

The DSC can over-rule the recommendation of the model in the light of other safety and tolerability information.

The primary statistical analysis will be conducted in R software.

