### **3.4.3 Stimulus Intervention levels:**

If marked sedation or apnoea  $>30\text{s}$  occurs, the following levels of stimulus intervention will be utilised and scored accordingly (0; no intervention).

1. Indirect noise e.g. door opening, closure, cough etc
2. Interrupt patient with direct speech
3. Touch
4. Unable to rouse patient with touch

Any intervention at level 4 or above will meet criteria for a DLT and a clinical decision will be made as to further action.

In the event of the need for clinical intervention, a crash trolley is available within the Clinical Research Facility, and a crash team is available at Hammersmith Hospital. Naloxone will be available in the ICRF as a rescue medication in the event of respiratory depression requiring intervention.

If further emergency clinical investigation and interventions are required, this will involve transfer to the emergency department at Charing Cross Hospital, via ambulance.

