**3.4.6 Evaluation window**

The evaluation window for primary and secondary outcome measures will begin at dosing and end at 5 hours post-dose, with the exception of the 'intervention level' (as defined in the DLT definition) which will begin at dosing and continue until the last follow-up phone call. This call will be conducted the following day, and the window will be extended if the participant is experiencing sedation or other symptoms.

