**3.4.7 Evaluable patient**

An evaluable participant is defined as one who has received study medication and has provided sufficient data to meet the primary endpoint of determining the presence or absence of a DLT, *and* sufficient data relating to the main secondary outcome measures. Whether sufficient data has been obtained for this purpose will be determined by clinical judgement on an individual participant basis.

In the unlikely event that a participant decided to self-discharge themselves after dosing but prior to the end of the 5 hour evaluation window, this participant could be counted as an evaluable patient with no DLTs provided they had completed the 2-3h timepoint and that this self-discharge had occurred within a clinical picture of stable or normalising observations. Attempts to complete the follow-up phone call would be made to confirm absence of DLT as defined by 'intervention level'.

In the event of an inability to acquire sufficient data, as defined above, the decision on whether to include an individual's data in the primary (DLT) or secondary analysis, or whether that individual would be replaced, would be made on a case by case basis.

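### The escalation rule in 8.3.2 reads visit data only, while 3.4.6 keeps one DLT criterion open until the follow-up call; nothing in the documents makes the dose decision wait

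*Combined protocol and SAP*

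**What the plan says.** **The escalation rule.** Section 8.3.2 reads: "Dose escalation will be based on the review of safety data during the experimental visit on the DLT evaluable safety set". It permits escalation only when the next lowest baclofen dose has been acceptable and "if no DLTs are observed for the current cohort of patients". The model is updated after at most every three patients, and doses may not be skipped. Section 4.4.2 likewise describes updating after each group of at most three. Section 9.3.3 adds that real-time data entry lets the Dose Setting Committee (DSC) update promptly.

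**The DLT window.** Section 3.4.2 makes an intervention level of 4 a DLT whenever it occurs; 3.4.3 defines level 4 as "Unable to rouse patient with touch". Section 3.4.6 ends the window at 5 hours for the other components, but for the intervention level sets one "which will begin at dosing and continue until the last follow-up phone call". That call is made the next day, and the window is extended for sedation or other symptoms. Section 5.5 provides a second call, later that day or the day after, for anyone still sedated. Section 2.10 closes the window at 5 hours for all outcomes and mentions the call only as further follow-up.

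**Evaluability.** Section 8.3.1.3 defines the DLT evaluable safety set as treated participants who can be evaluated for a DLT. Section 3.4.7 says of the data needed: "Whether sufficient data has been obtained for this purpose will be determined by clinical judgement on an individual participant basis".

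**The concern.** The protocol extends one of its five DLT criteria beyond the visit, but its escalation rule names the visit as the data source. If the rule is followed as written, the next group's dose can be fixed while that criterion is still open for the current group. An unobserved DLT can only make the current group look safer than it was. The two drugs are both CNS depressants, and the intervention level is the criterion that captures loss of responsiveness. The gate to a higher dose should therefore use the same window as the DLT definition.

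**Working it through.** **1. Is there a waiting rule?** Sections 2.10, 3.4.6, 3.4.7, 4.4, 4.4.2, 5.3.1, 8.3.1.3, 8.3.2, 9.1, 9.3.3 and 12 (Trial Management) were compared. They give the group size, the update after each group and the committee's role. None gives a minimum interval or makes completion of the call a condition.

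**2. Does the evaluable set supply one?** Not reliably. Under 3.4.7 an early self-discharger can be included: "this participant could be counted as an evaluable patient with no DLTs provided they had completed the 2-3h timepoint", given a reassuring clinical course. The call is then something to be tried: "Attempts to complete the follow-up phone call would be made to confirm absence of DLT". It is not a condition of evaluability or of the dose decision.

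**3. What is exposed?** Only a first level-4 event after the visit; NEWS2, respiration, GCS and QTc are closed at 5 hours.
- Baclofen peaks 88-102 minutes after dosing (5.4.3).
- Methadone peaks 1.8-3.8 h after its dose, which is taken 40-60 minutes before baclofen (5.4.2). Relative to baclofen that is 1.8 h - 60 min = 0.8 h to 3.8 h - 40 min = 3.1 h.

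Both peaks fall inside the 5-hour stay.

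**4. Illustration of size.** The plan has no figure to reproduce. Let p be the true DLT risk and f the share of DLTs that first appear after the visit. The documents do not give f; 5-20% is an assumption. Suppose visits fall on different days, so that only the last of three calls is outstanding at the decision.

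P(no DLT seen in 3) = (1 - p)² × (1 - p(1 - f))

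| f | p = 0.25 | p = 0.15 |
|---|---|---|
| 0 | 0.75³ = 42.2% | 0.85³ = 61.4% |
| 5% | 0.5625 × 0.7625 = 42.9% | 0.7225 × 0.8575 = 62.0% |
| 10% | 0.5625 × 0.7750 = 43.6% | 0.7225 × 0.8650 = 62.5% |
| 20% | 0.5625 × 0.8000 = 45.0% | 0.7225 × 0.8800 = 63.6% |

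The increase is (1 - p)² × p × f. At p = 0.25 this is 0.1406 × f: 0.7 percentage points at f = 5%, 2.8 at f = 20%, and 0.1 at f = 1%.

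Seeing no DLT in the group is necessary for escalation but not sufficient: the model's safety rule and the ban on skipping doses still apply.

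**The case against.** **The definitions can be read together.** Escalation uses the DLT evaluable set; evaluable means having enough data to determine whether a DLT occurred; and the DLT includes a criterion that runs to the last call. On that reading, someone whose call is outstanding is not yet evaluable. The self-discharge clause is an exception for an unlikely event, and it treats the call as confirming that there was no DLT. This reading is reasonable but does not settle the matter: evaluability is left to clinical judgement, and the same sentence of 8.3.2 names the visit as its data source.

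**The detailed SAP may contain the rule.** This stands. A reader might infer that the trial has no waiting rule at all. The documents do not support that; they show only that the protocol text contains none.

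**Safeguards would catch such an event.** Discharge needs the study physician's approval, and participants leave with a round-the-clock number for the study doctor (5.4.15). An event of this gravity would very likely be an SAE, with a form due within 24 hours and same-day reporting if fatal or life-threatening (10.1.5 and the SAE text after it). The DSC can over-rule the model. All this stands and is the main reason the point is small. It does depend on the event being known before the next dosing. The dose is recommended at randomisation (5.3.1), and later re-allocation is described only for rescheduled or replacement participants (5.3.1, 5.8.1).

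**A telephone call cannot score level 4.** True: the criterion requires someone to apply touch. The call could only elicit a report of such an event.

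**Conclusion.** The mismatch is real on the text, and it is minor. Sections 8.3.2 and 3.4.6 use different windows for a dose decision, and 2.10 agrees with neither the exception nor the extension in 3.4.6. The conclusion rests on the documents supplied; a timing rule in the detailed SAP would reduce it to a wording conflict.

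The effect is probably very small. The figures above depend on an assumed f and are not evidence that late DLTs occur; values of f below 5% are plausible.

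Three stronger readings do not hold:
- *Late DLTs are lost.* They are not: a late DLT enters the next model update. Only the decision taken in between is exposed.
- *The gate is weakened substantially.* If all three calls were outstanding, the 25%-risk figure would be (1 - p(1 - f))³ = 44.3-51.2% for f = 5-20%. But no section describes three visits on the same day, and each visit lasts 6-7 hours at one facility (5.4).
- *Earlier next-day effects show that late DLTs are likely.* Section 7.1.1 reports mild effects still felt the next day in one healthy volunteer at 90mg, and none in the alcohol-dependent group. That is far from level 4.

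**What to change.** - **8.3.2 and 4.4.2:** state that escalation uses DLT data to the end of the 3.4.6 window, and that the model update and the next group's dose release follow the last follow-up call of every participant in the current group, including any repeat call for persisting sedation.
- **Participants not reached:** set a short limit, after which the DSC decides evaluability under 3.4.7. Two days after dosing would be one choice, since 5.5 allows a second call on the day after the first; the exact limit is for the sponsor.
- **2.10:** add the intervention-level exception so that it agrees with 3.4.6.
- **Detailed SAP:** check that it carries the same rule.

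**Cost:** a few sentences and no extra visits or calls, because the next-day call is already scheduled for everyone. The delay is about one day per group. With 48 baclofen participants in full groups of three, 48/3 = 16 groups, so roughly 16 days in total. It would be longer if groups are smaller, a window is extended or someone cannot be reached.

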Outcome measures that will be used to determine the incidence of a DLT will include oxygen saturation, respiratory rate, cardiovascular measures (ECG, blood pressure) and CNS effects (sedation, alertness). End tidal CO2 and adverse events will also be monitored.

The adaptive Bayesian model will be regularly updated (after each group of up to 3 participants administered baclofen) given the observed patients' responses, providing efficiency in decision-making, by recommending the most likely safe target individualised dose. The study can therefore be stopped earlier for safety if the model suggests that 30mg of baclofen and 60mg of methadone is highly likely to be *unsafe*. The study can also stop earlier if the highest dose of baclofen (90mg) is highly likely to be *safe*, i.e. shows no DLTs with 120mg of methadone, provided that the study has also achieved sufficient data to meet secondary endpoints.

In addition to the approach described above, an evaluation of pharmacokinetic parameters will be investigated through regular blood sampling and assay of baclofen and methadone plasma concentrations. The pharmacodynamic effects of baclofen relative to placebo, and their dose separation will be determined through objective (plasma growth hormone concentrations) and subjective measures (visual analogue scales and questionnaires for drug effects, anxiety, sleep). The potential for abuse liability, relative to placebo, will be assessed using the Drug Effects Questionnaire.

GABA-B receptor sensitivity will be determined through comparison of pharmacodynamic effects in comparison with historical healthy controls, using data derived from previous work using comparable measures and time-points at the 10 and 60mg baclofen dose levels (Durant et al., 2018).

**Primary & secondary endpoints:** If we find that all dose levels of baclofen are safe up to and including 90mg in combination with 120mg methadone (primary endpoint), the study can still continue up to the maximum sample size to achieve maximum precision for secondary outcomes, explore more methadone doses (<120mg) in a variety of participants and baclofen dose-response separation, as required.

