### 4.4 Treatment algorithm

A Bayesian dose-escalation adaptive model will be used to determine the baclofen dose allocation and will be informed by the occurrence of dose-limiting toxicity (DLT) events at increasing doses of baclofen (10, 30, 60, 90mg). Participants will be randomised (single-blind) to baclofen or placebo in a 3:1 ratio. If allocated to baclofen, the adaptive model will recommend the dose level for a given patient according to their prescribed dose of methadone and prior information regarding the incidence of DLTs. The model will be updated after each group of up to 3 participants, according to the observed patients' responses. The Dose setting committee (DSC) retains the ability to override the algorithms dose recommendation if clinically indicated.

The study can therefore be stopped earlier for safety if the model suggests that 30mg of baclofen and 60mg of methadone is highly likely to be *unsafe*. The study can also stop

earlier if the highest dose of baclofen (90mg) is highly likely to be *safe*, i.e. below the target toxicity with 120mg of methadone, provided that the study has also achieved sufficient data to meet secondary endpoints.

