#### 4.4.2 Baclofen dose decisions

The lowest dose of baclofen (10mg) will be allocated to the first group of 3 participants assigned to receive baclofen. The dose-toxicity model will be continuously updated after each group of at most 3 participants, to recommend dosing for the subsequent group of participants. The model will describe the probability of a patient experiencing a DLT;  $p(\text{DLT})$ , at a given methadone-baclofen dose, the probability of the given dose being safe;  $p(\text{safe})$ , and the probability of the dose being within the target toxicity interval;  $p(\text{target})$ .

The model will establish the combination-toxicity relationship which borrows information between different doses across both drugs, leading to an efficient use of data. The model will output the dosing function that provides the safe dose of baclofen that is most likely to be associated with 15-25% DLT risk for a given dose of methadone.

According to the model, if any of these DLTs are met, then the next group of patients will be assigned to the current (or lower) dose of baclofen, without dose escalation,

depending on the prescribed dose of methadone for the next individual that enters the study.

If there is no DLT, a dose escalation may be advised by the model, again, depending on the prescribed dose of methadone for the next individual that enters the study.

The model will recommend to stop the trial earlier due to safety concerns if the probability that the risk of DLT for 60mg of methadone in combination with 30mg of baclofen exceeds the target range is 25% or more. The model will recommend to stop the trial earlier due to all doses of baclofen being safe if the probability that the risk of DLT for 120mg of methadone in combination with 90mg of baclofen does not exceed the target range is 92.5% or more, representing the 'all-safe-stop criteria'.

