The Dose Setting Committee (DSC, comprised of a statistician, clinician and member of the research team) can decide to over-ride any recommendation made by the model, if clinically indicated. Outside of the model parameters, clinical judgement will determine whether responses to baclofen are sufficiently concerning to cease escalation, escalate to a lower dose than planned by the model, or to reduce the average methadone dose for each dose of baclofen examined. If doses of 90mg baclofen are deemed safe by the model with up to and including 120mg methadone, further escalation will cease provided that the data required for secondary endpoints are met.

Should the study team witness multiple DLTs, using their clinical experience they can halt the trial early over safety concerns.

In the scenario that there is a very high probability that all doses are safe before reaching the maximum recruitment of n=48 receiving baclofen, the study will retain the ability to override the all-safe-stop criteria to continue recruitment until we have tested a sufficient range of doses of methadone to ensure we have covered the clinical range of potential methadone doses and/or to explore baclofen dose separation to achieve maximum precision on secondary outcomes.

Given no safety concerns, we expect the *minimum* numbers of participants at each of the doses to be as follows: n=3 @ 10mg baclofen, n=3 @ 30mg baclofen, n=12 @ 60mg baclofen and n=12 @ 90mg baclofen, with n=10 receiving placebo, providing sufficient data to allow adequate exploration of dose separation on primary and secondary outcomes across a range of methadone dose levels, and an assessment of GABA-B receptor sensitivity and any gender effects. These numbers might be exceeded if the variability in response is larger than anticipated, female representation is lower than we would like, or we have not yet been able to test the full range of methadone doses. If a particular baclofen dose is deemed unsafe, then the lower doses would be similarly explored.

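### The all-safe stopping recommendation rests on one model estimate at 90 mg baclofen with 120 mg methadone, and no patient near that methadone dose is required

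*Combined protocol and SAP*

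**What the plan says.** Section 8.3.2 allows an early stop with all baclofen doses found safe "if the probability that the risk of toxicity at 90mg baclofen in combination with 120mg methadone is 25% or below, is above 92.5" per cent. Section 4.4.2 gives the same rule. Neither section asks for any number of patients at or near that combination. Section 4.4.2 says the model "borrows information between different doses across both drugs".

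Several provisions stand between this recommendation and an actual stop:
- The stop applies "provided that the study has also achieved sufficient data to meet secondary endpoints" (section 4.4; also 2.10). One secondary objective in 3.1.2 concerns response at different methadone levels.
- The Dose Setting Committee can over-rule the model (4.4.2, 8.3.2), and a DMC meeting reviews the decision (9.1).
- Section 4.4.2 says "the study will retain the ability to override the all-safe-stop criteria to continue recruitment until we have tested a sufficient range" of methadone doses, the aim being "to ensure we have covered the clinical range of potential methadone doses". It gives no number of patients and no methadone band.
- The expected minimum numbers in 4.4.2 are set by baclofen dose, including "n=12 @ 60mg baclofen and n=12 @ 90mg baclofen". They may be exceeded if the full methadone range has not been tested.
- Section 6.1 promises an effort to recruit across the methadone range, and 9.1 permits targeting a methadone dose.

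Section 2.10 describes the same stop by saying that 90 mg "shows no DLTs with 120mg of methadone". It presents the remaining work as being to "explore more methadone doses (<120mg) in a variety of participants", as though 120 mg had already been tested.

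**The concern.** The stated target in 3.1.1 is 90 mg baclofen with methadone up to 120 mg. Section 2.10 expects risk to rise with methadone dose and names respiratory depression as the main DLT concern. The expected mean methadone dose is about 53 mg (2.10), and most local clients take less than 60 mg (3.1.1). A finding of safety at 100 to 120 mg could therefore come mainly from the assumed shape of the dose-toxicity model, because nothing obliges the trial to observe that range.

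The planned detoxification population, below 40 mg methadone (3.1.1), is not affected. What is at stake is the wider claim, which matters because Table 1 shows the follow-on trial taking its methadone dose from this study.

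**Working it through.** **What can be reproduced.** The 92.5% is a chosen threshold. Priors and simulation results are not in the documents; 8.3.2 defers the model specification to a separate detailed SAP. The operating characteristics therefore cannot be reproduced, and everything below rests on stated assumptions.

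**1. Coverage at high methadone without targeting.** The inputs are a mean of 53 mg (2.10) or 56.3 mg (3.1.1) and a range of 5 to 120 mg (2.10). The assumption is a truncated normal with SD parameter 20 to 35 mg.
- Share p of patients at 100 mg or more: 0.9% to 6.8%.
- Expected number among the 12 at 90 mg baclofen: 12p = 0.1 to 0.8.
- Chance of none among those 12: (1 − p)^12 = 90% at the low share and 43% at the high share.

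**2. Can the threshold be met by extrapolation?** The model is the usual 5-parameter combination form for baclofen dose b and methadone dose m: odds = (o1 + o2 + o1·o2)·exp(η·(b/90)·(m/120)), with log o1 = a1 + β1·log(b/90) and log o2 = a2 + β2·log(m/120). The assumed priors are a ~ N(logit p0, s²) for each drug, log β ~ N(0, t²) and η ~ N(0, u²). Five sets (p0; s; t; u) were used: (5%; 1.5; 0.7; 0.8), (7.5%; 1.5; 0.7; 0.8), (10%; 1.5; 0.7; 0.8), (5%; 2.0; 1.0; 1.12) and (10%; 1.0; 0.7; 0.8).

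Before any data, these give P(risk at 90/120 ≤ 25%) of 49% to 70%, so the prior alone does not meet the rule. They give P(risk at 30/60 > 25%) of 9% to 22%, so the 25% safety stop is not met at the start either.

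The data are no DLT in 3, 3, 12 and 12 patients at 10, 30, 60 and 90 mg baclofen (the 4.4.2 minimum plan), with three spacings of methadone doses below a cap. This makes 5 × 3 = 15 cases.

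| Nobody above (methadone) | P(risk at 90/120 ≤ 25%) | Cases above 92.5% |
|---|---|---|
| 90 mg | 94–98% | 15 of 15 |
| 80 mg | 92–98% | 14 of 15 |
| 70 mg | 91–97% | 12 of 15 |
| 60 mg | 89–96% | 8 of 15 |

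**3. Sensitivity to the prior.** A wider grid of 94 assumed prior sets used both 60/60 and 90/120 mg as reference doses and placed all 30 patients, without a DLT, on a single methadone dose. The rule was met in 77 of 94 sets at 60 mg, 57 at 53 mg, 34 at 40 mg and 17 at 25 mg.

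**4. How likely are the caps in step 2?** Under the step 1 distributions, the chance that none of 30 untargeted patients exceeds 90 mg is about 1.5% to 40%. For 80 mg it is under 7%, and for 70 mg or 60 mg under 0.2%. This is a different event from step 1, which concerns only the 12 patients on 90 mg baclofen.

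**5. What three patients would add.** To the 90 mg cap data, add 3 patients on 90 mg baclofen with 110 mg methadone.
- 0/3 DLTs: posterior 97–99%, 15 of 15 cases still pass.
- 1/3: about 85–94%, 3 of 15 pass.
- 2/3: 53–79%, none pass.

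The chance of at least one DLT in 3 is 1 − 0.65³ = 73% at a true risk of 35%, and 1 − 0.95³ = 14% at 5%. A clean cohort occurs with probability 0.75³ = 42% at a true risk of 25%.

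**6. Section 2.10 against 8.3.2.** Section 2.10's gloss is an observed count of zero. Section 8.3.2's rule is a posterior probability, which can pass with nobody at 120 mg and need not fail after one DLT there.

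**The case against.** The strongest reply is that the rule only recommends. Secondary-endpoint data, the Dose Setting Committee and a DMC review all come before a stop, and 4.4.2 already states the aim of covering the clinical methadone range. This stands, and it lowers the severity. It does not remove the point, because no safeguard sets a minimum at high methadone.

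The second reply is that the illustrated data are uncommon and depend on the prior. This also stands. Nobody above 80 mg among 30 patients is unlikely by chance, recruitment is not meant to be left to chance, every case in the table assumes no DLT, and all five priors there take 90/120 as the reference combination. The detailed SAP may also contain a coverage condition. A reader might infer that the trial will probably stop with no high-methadone patients at all, or that any reasonable prior would trigger the rule. The documents support neither.

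Third, 2.10 might be read as setting a rival stopping rule. Its operative words are that the dose be highly likely to be safe; only the explanatory gloss differs, and it sits in a summary. It is a wording slip.

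Finally, three patients discriminate poorly. That is fair: 0/3 moves the illustrated posterior only from 94–98% to 97–99%. The value lies in giving a DLT at high methadone a chance to be seen.

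**Conclusion.** The point holds in a limited form. As written, the all-safe criterion can be met by extrapolation, and nothing binding requires a patient near 120 mg methadone on 90 mg baclofen. That part follows from the text alone. The size does not: the 43% to 90% chance of no such patient among the 12 depends on an assumed methadone spread and no targeting, and the pass counts depend on assumed priors and no DLTs.

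It would go too far to say that the trial lacks safeguards or that its dose escalation is unsafe. The consequence is confined to how firmly safety at roughly 100 to 120 mg methadone may be claimed. The change is worth making because it turns an aim the protocol already states into a condition; the 2.10 correction is minor.

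**What to change.** 1. In 8.3.2 and 4.4.2, add to the all-safe criterion: *and at least 3 DLT-evaluable patients prescribed 100–120 mg methadone have received 90 mg baclofen*. Reach this through the targeting that 9.1 already allows, within the maximum of 48 on baclofen.
2. If this is not reached by 48, state the highest methadone dose actually tested with 90 mg baclofen. Report the safety estimate above it as model extrapolation and do not describe it as a dose found safe.
3. In 2.10, replace "shows no DLTs with 120mg of methadone" with the 8.3.2 criterion.

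The wording itself costs nothing. The minimum plan uses 3 + 3 + 12 + 12 = 30 of 48 baclofen places, leaving 18, so one cohort of 3 fits. The patients must be sought, however. Doses cannot be skipped, so with cohorts of 3 at most 48 − 9 = 39 places can be at 90 mg; keeping 12 at 60 mg leaves 48 − 18 = 30. Without targeting, the binomial chance of fewer than 3 patients at 100 mg methadone or more in those 30 to 39 places is about 50% to over 99%. If they cannot be found, no extra patients are needed but the claim narrows. If the combination is truly safe, a clean cohort leaves the recommendation in place, although at a true risk of 5% there is still a 14% chance of a DLT among the three that could delay it.
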